- Any record of pregnancy or breast feeding at the time of treatment initiation.

Patients with medication errors:

- Prescribed and/or administered > 1 dose per week of dulaglutide (6).
- The number of doses/week will be calculated by measuring the time span between the current prescription and the next one (in weeks) and dividing the number of injections prescribed in the current prescription by this time span. This number of doses/week will be used in the cross sectional study as an attribute of the prescription to assess the occurrence of medication errors as described above.

Patients with off-label use:

- Prescribed dulaglutide with no diagnosis of T2DM as defined above, at the beginning of this list of subgroups of populations.
- Prescribed dulaglutide with a diagnosis of T2DM as defined above and without a record of other ADMs during the 6-month baseline period, i.e. dulaglutide was prescribed as first-line therapy.

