9.3.1. Outcomes/Measurements of Interest

The following variables will be analysed in each subgroup of interest and among patients initiated with dulaglutide (Table 9.3.2-1):

- Patients' demographics (age and gender) at baseline
- Relevant comorbidities
- Medical history: disease diagnoses (using appropriate disease classification)
- Concomitant ADMs
- Other drug exposures (main therapeutic classes)
- Average daily dosage of prescriptions
- Prescriptions in combination with other ADMs

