Dulaglutide Country: Sweden	Subgroups of interest				
Outcomes/measurements of interest	1. Patients with severe renal failure (N=xx)	2. Patients with hepatic disease (N=xx)	...	9. Patients with off-label use (N=xx)	10. All (N=xx)
Dulaglutide exposure Average daily dose Missing Mean (SD) Min-Max Median [Q1- Q3]	xx (xx.x%)	xx (xx.x%)		xx (xx.x%)	xx (xx.x%)

Mock Table for the Description of the Use of Dulaglutide - Primary Objective: Description of the Use of Dulaglutide per Subgroups

Dulaglutide Country: Sweden	Subgroups of interest				
	1. Patients with severe renal failure (N=xx)	2. Patients with hepatic disease (N=xx)	...	9. Patients with off-label use (N=xx)	10. All (N=xx)
Concomitant medications (at index date) Anti-diabetic treatments:	xx (xx.x%)	xx (xx.x%)		xx (xx.x%)	xx (xx.x%)

 • Insulins and analogues (short- and long-acting, for injection and inhalation) (meal-time, for example, Insulin Lispro; and basal, for example Insulin Glargine). • Biguanides (for example, Metformin) • Sulfonylureas (for example, Glipizide) • Alpha-glucosidase inhibitors (for example, Acarbose) • Thiazolidinediones (for example, Pioglitazone) • Dipeptidyl peptidase-4 inhibitors (for example, Sitagliptin) • Sodium glucose cotransporter-2 (SGLT2) inhibitors (for example, Empagliflozin) • Other GLP-1 RA • Meglitinides (for example, Repaglenide) • Amylin analogues (for example, Pramlintide) 	xx (xx.x%)	xx (xx.x%)		xx (xx.x%)	xx (xx.x%)
And:					

 • Single-pill combinations of oral ADMs • Single-injection combinations of insulin and GLP-1 RA (for example, Insulin Degludec and Liraglutide) 	xx (xx.x%)	xx (xx.x%)		xx (xx.x%)	xx (xx.x%)
	xx (xx.x%)	xx (xx.x%)		xx (xx.x%)	xx (xx.x%)

Concomitant medications (at index date) Other treatments (main classes)	xx (xx.x%)	xx (xx.x%)		xx (xx.x%)	xx (xx.x%)
Dulaglutide off-label use - Patients without T2DM - Patients with T2DM for whom dulaglutide was prescribed as first-line therapy	xx (xx.x%) xx (xx.x%) xx (xx.x%)	xx (xx.x%) xx (xx.x%) xx (xx.x%)		xx (100%) xx (xx.x%) xx (xx.x%)	xx (xx.x%) xx (xx.x%) xx (xx.x%)
Medication history (at baseline period) Anti-diabetic treatments: - specific classes	xx (xx.x%)	xx (xx.x%)		xx (xx.x%)	xx (xx.x%)
Medication history (at baseline period) Other treatments: - specific classes	xx (xx.x%)	xx (xx.x%)		xx (xx.x%)	xx (xx.x%)

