- Since it will not be possible to distinguish between patients that were appropriately prescribed dulaglutide monotherapy (ie, when diet and exercise alone did not provide adequate glycaemic control and the use of metformin was considered inappropriate due to intolerance or contraindications) and patients who were prescribed monotherapy inappropriately (i.e. did not meet these criteria), the number of patients found to be taking off-label first line dulaglutide will be an overestimate of the number of actual patients taking off label first line dulaglutide.
- Medication errors will be evaluated based on the time span between the first prescription and the next one. In a number of cases the next prescription will not be still captured in the database. These cases will be considered as missing data for the analysis of medication errors. Other sources of bias:
 - **Selection bias:** in some databases (for example, French and German DA) the sample of physicians are representative of the physicians in each country in terms of the stratification factors used to select the panel. However, it is not known whether the physicians who belong to the panel have the same prescription behaviour as the physicians who are not part of the panel, especially those who were invited to take part but refused. Similar considerations can be expressed for physicians who belong for a long time and physicians recently included in the panel. To control these biases as much as possible, the distribution of the strata in each data base will be compared to the distribution of strata of the corresponding physicians' population in the country. This limit does not apply to the Swedish cohorts because of their exhaustiveness.
 - **Misclassification bias:** Misclassification bias can result if study subjects are not categorised correctly with regards to exposure or selected patient characteristics. Since the data bases are fully anonymised, it is impossible to verify the information with source data. This bias cannot be controlled as there is no possibility to check the information in databases. For example, the definition of severe renal failure is based on eGFR. However, this value may not be recorded relevantly in the database. Consequently, there may be false negatives of severe renal failure, that is, those with this condition who are classified as not having the severe renal failure.

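### Off-label use in T2DM is defined by prior treatment ('first-line') but judged in section 9.9.1 by monotherapy; the two groups differ in both directions and the plan does not cross them

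*Protocol*

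**What the plan says.** Section 9.3 gives off-label use two branches. One is "Prescribed dulaglutide with no diagnosis of T2DM as defined above". The other is T2DM treated with dulaglutide "without a record of other ADMs during the 6-month baseline period, i.e. dulaglutide was prescribed as first-line therapy". Table 9.3.2-1 and the mock Table 9.7.4-1 repeat the second branch as "Patients with T2DM for whom dulaglutide was prescribed as first-line therapy".

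Section 9.9.1 explains the weakness of that branch. It says that "it will not be possible to distinguish between patients that were appropriately prescribed dulaglutide monotherapy" (diet and exercise insufficient, metformin considered unsuitable) and patients given monotherapy without meeting those conditions. It concludes that "the number of patients found to be taking off-label first line dulaglutide will be an overestimate" of the true number. No other direction of error is mentioned.

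Two further outputs matter here. "Prescriptions in combination with other ADMs" and concomitant ADMs are listed measurements, overall and in each subgroup (sections 9.3.1 and 9.7.4). Section 9.7.4 defines concomitant drugs as those prescribed at the index date and medication history as drugs recorded in the six months before. The mock table shows the two as separate blocks by drug class.

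**The concern.** The classification looks backwards, at what the patient took before dulaglutide. The account of appropriateness looks sideways, at what the patient takes with it. If these select different patients, the off-label count does not match the criterion that the protocol uses to interpret it, and the stated bias covers only part of the discrepancy.

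This matters because off-label use is a subgroup in the primary objective and is the whole of the secondary objective. The same definition is applied in every country and every yearly wave, so a mismatch would run through all of the off-label results.

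**Working it through.** No stated figure is in question, so the check is a cross-classification. Take all T2DM initiators and classify them by other ADM in the six-month baseline and other ADM at initiation. Then apply the section 9.3 rule and the section 9.9.1 notion of monotherapy to each cell.

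| Cell | ADM in baseline | ADM at initiation | Off-label under 9.3 | Dulaglutide alone (9.9.1) |
|---|---|---|---|---|
| A | yes | yes | no | no |
| B | yes | no | no | yes |
| C | no | yes | yes | no |
| D | no | no | yes | yes |

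The T2DM off-label count is C + D. The monotherapy group is B + D. The two agree in A and D and disagree in B and C.

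**Can the planned tables show B and C?** The mock table has no row for dulaglutide alone and does not cross baseline history with ADMs at the index date. The class rows can overlap, so adding them up does not help. If the heading row of the index-date ADM block means 'any ADM', B follows by subtraction between the 'All' and off-label columns:

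B = (N_All − any_All) − (N_off − any_off)

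Patients without T2DM and without an ADM at the index date appear in both brackets and cancel. The layout as available does not settle whether the heading row carries that meaning. Even if it does, two limits remain:
- C is not isolated, because the off-label column also contains patients without T2DM, some of whom may have an ADM at the index date.
- The subtraction works only for all initiators. Within a population of interest, such as severe renal failure, the table gives no index-date ADMs for the off-label members of that column. That is the level at which the secondary objective is set.

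**How much could it matter?** The documents give no shares for any cell. The following is an illustration on assumed values only. Write d, c and s for cells D, C and B as shares of T2DM initiators.
- Share of monotherapy patients outside the off-label count = s / (d + s). With d = 10% and s = 2%: 2/12 = 17%. With d = 5% and s = 20%: 20/25 = 80%.
- Share of the T2DM off-label count not on monotherapy = c / (c + d). With c = 1% and d = 5%: 1/6 = 17%. With c = 2% and d = 10%: 2/12 = 17%. The equality comes from the assumed ratio.
- Per 1,000 with d = 10%, c = 2%, s = 2%: off-label count 100 + 20 = 120; monotherapy 100 + 20 = 120. The totals match, yet 20 patients are in one group only and another 20 in the other only.

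The spread from 17% to 80% shows that the result depends entirely on the assumed inputs.

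**The case against.** The strongest case against has four parts.

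1. *The definition is consistent.* Sections 9.3, 9.3.2 and 9.7.4 all give the same two categories, and the conclusion in 9.9.1 is confined to first-line use. A reader might infer from 9.9.1 that every previously treated patient moved to dulaglutide alone is off-label. The documents do not say so: on the protocol's own account such a patient may be treated appropriately, and the data cannot tell. Nor is the stated overestimate wrong; as worded, for first-line use, it holds. What stands against the plan is that 9.9.1 argues from monotherapy to first-line without saying that the groups differ.

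2. *The patients are not invisible.* A reader might infer that use of dulaglutide alone will never be shown. That goes too far. Combination use and index-date ADMs are planned outputs, and the overall share on dulaglutide alone is the complement of the first. What is missing is the link to baseline history.

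3. *Table rows belong to the SAP.* Section 9.7.5 leaves table shells to the SAP, and the note under Table 9.7.4-1 allows the structure to change. A missing row would therefore not be a finding by itself. The definition and the bias statement, however, are fixed in the protocol, and the SAP is to be based on it.

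4. *Looking past the index date adds follow-up to a cross-sectional design.* This has some force, but the medication-error definition in section 9.3 already uses the interval to the next prescription.

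**Conclusion.** The concern holds as a mismatch between a definition and its interpretation. The first-line rule and the monotherapy criterion disagree in two of the four cells, in opposite directions: B is left out of the off-label count and not displayed as a group, and C is counted although not on monotherapy. Section 9.9.1 describes neither.

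The size cannot be estimated from the documents, and the percentages above are not estimates. They also refer to all patients on dulaglutide alone, including those treated appropriately, so they must not be read as the share of off-label use that is missed. The study remains valid as a description of use. The change should be made because the definition drives a primary-objective subgroup and the secondary objective.

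**What to change.** - Reconcile section 9.3, Table 9.3.2-1, Table 9.7.4-1 and section 9.9.1 so that they refer to the same patients. Which use counts as off-label is for the sponsor to settle.
- Within T2DM initiators, report the two-by-two of other ADM in the baseline (yes/no) by other ADM at initiation (yes/no), overall and in each population of interest. This makes two groups visible: 'previously treated, dulaglutide alone', labelled as appropriateness not assessable and kept outside the off-label total, and 'no baseline ADM, started with another ADM'.
- State in 9.9.1 that, relative to the monotherapy criterion, the first-line rule can both over-count and miss patients.

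The cost is one derived variable and a small table. Table 9.4.5-1 lists co-prescriptions, treatment history and duration of exposure as available in all five databases.

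The main difficulty is measurement. An ADM continued on a prescription issued before the index date can look stopped if only index-date prescriptions are read. The window for 'ADM at initiation' must therefore be stated and must allow for ongoing supply. Any part of the window after the index date may count later add-ons as concomitant and will leave some late initiators missing. For example, with the six-month lag listed for Sweden, an extraction in Q2 2017 reaches at most about the end of 2016, the end of the initiation period for the second wave.

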9.3.1. Outcomes/Measurements of Interest

The following variables will be analysed in each subgroup of interest and among patients initiated with dulaglutide (Table 9.3.2-1):

- Patients' demographics (age and gender) at baseline
- Relevant comorbidities
- Medical history: disease diagnoses (using appropriate disease classification)
- Concomitant ADMs
- Other drug exposures (main therapeutic classes)
- Average daily dosage of prescriptions
- Prescriptions in combination with other ADMs

9.3.2. Collected variables

To assess the above subgroups and measurements of interest, several variables will be extracted from each database whenever available: demographics, medical history, treatment, clinical and clinical laboratory data on patients. These variables along with their corresponding International Classification of Disease, 10th version (ICD-10) codes are presented in this protocol (Table 9.3.2-1). For CPRD database, the corresponding Read codes will be specified in the statistical analysis plan (SAP).

Table 9.3.2-1. Variables, Subgroups and Measurements of Interest in Dulaglutide Initiators

Variable, subgroup or outcome/measurement	Definition and categories*
Patients demographics at initiation of dulaglutide use: Age Gender BMI categories, Countries	< 18, 18-44, 45-64, 65-74, ≥75 years Male or Female Weight (kg) / Height (cm) ² < 18.5, 18.5-25, 26-30, > 30 kg/m ² UK, Germany, Sweden (or Spain and France)
Co-morbidities , at initiation of treatment to identify the subgroups of interest: 
 • History of severe renal failure • Heart failure • Hepatic disease • Severe gastrointestinal disease • Children and adolescents • Elderly • Pregnant women • Breastfeeding women 	ICD-10 code N18.5, N18.5 ICD-10 codes I50, I11, I13 ICD-10 codes B18, K70-K77, C22 ICD-10 codes C15-C26 K22.0, K22.1, K22.2 -K22.6, K23-K28, K29.0, K29.4 K50, K51, K55, K57 Age < 18 (subgroups: 0-4, 5-9, 10-14, 15-17 years) Age ≥ 75 ICD-10 codes: A34, E23.0, F53, M83, O00-O99, O24.1, O24.3, O24.9, Z32-Z36, Z39 Z39.1
Lab tests values (if available): 
 • Haemoglobin A1c (HbA1c) • e-GFR • Serum Creatinine Urine albumin/creatinine ratio (UACR) 
 • LDL-C (LDL-cholesterol) • HDL-C (HDL-cholesterol) • AST/ALT • Bilirubin • Beta hCG 	Abnormal values: < 6.5%, ≥6.5% eGFR value < 30 ml/min/1.73 m ² < 120, ≥120 µmol/L or mg/dL (male) < 100, ≥100 µmol/L or mg/dL (female) UACR >30 mg/g: albuminuria present: < 1.6, ≥ 1.6 g/L < 0.35 g/L, ≥0.35 g/L ≤ 2 or > 2 times upper limit of the normal range < 2, >7mg/L Positive

Variables, Subgroups and Measurements of Interest

Variable, subgroup or outcome/measurement	Definition and categories*

Other comorbidities frequent in T2DM patients: Dyslipidemia Hypertension
 
Macrovascular complications: Ischaemic heart disease
 
Stroke Peripheral arterial obstructive disease
 
Microvascular complications: Diabetic neuropathy Diabetic retinopathy Diabetic nephropathy
	
ICD-10 codes E78 or lipid modifying agents (ATC C10) ICD-10 codes I10-I15 or antihypertensives (ATC C02, C03, C04, C07, C08, C09) with no angina pectoris (I20, I25)
 
ICD-10 codes I20-I25 or antiangina agents (ACT C01D, C07, C08, C09) I61-I64 I70.2
 
G62.9 H36.0 N08.3

Solid tumours (Cancer)
 
 • liver • pancreas • endometrium • colon • rectum • breast • bladder 	
ICD-10 codes C220-C229 ICD-10 codes C250-C259 ICD-10 code C541 ICD-10 codes C182-C189 ICD-10 code C20 ICD-10 codes C500-C509 ICD-10 codes C670-C679

Dulaglutide dose: per 0.5 ml
	
Dose: 0.75 mg / week 1.5 mg / week >1.5 mg / week

Variables, Subgroups and Measurements of Interest

Variable, subgroup or outcome/measurement	Definition and categories*
Concomitant medications for T2DM , at index date of dulaglutide initiation	
 • Molecule: INN/brand name • ATC code or associated medcode for AMD 
A10A Insulins and analogues
 
 ○ A10AB Insulins and analogues for injection, fast-acting ○ A10AC Insulins and analogues for injection, intermediate-acting ○ A10AD Insulins and analogues for injection, intermediate- or long-acting combined with fast-acting ○ A10AE Insulins and analogues for injection, long-acting ○ A10AF Insulins and analogues for inhalation 
A10B Blood glucose lowering drugs, excluding insulins
 
 ○ A10BA Biguanides ○ A10BB Sulfonylureas ○ A10BD Combinations of oral blood glucose lowering drugs ○ A10BF Alpha glucosidase inhibitors ○ A10BG Thiazolidinediones ○ A10BH Dipeptidyl peptidase 4 (DPP-4) inhibitors ○ A10BX Other blood glucose lowering drugs (exenatide, liraglutide, lixisenatide, albiglutide), excluding insulins 
A10P SGLT2 Inhibitors

Other concomitant medications , at index date of dulaglutide initiation	
 • ATC codes or associated medcode for main pharmacological classes.
History of medications for T2DM , during 6-month baseline period	
 • ATC code or associated medcode for anti-diabetes medications (see above)
History of other medications , during 6-month baseline period	
 • ATC code or associated medcode for main pharmacological classes.
Off-Label Use	
 • Patients without T2DM • Patients with T2DM for whom dulaglutide was prescribed as first-line therapy

Variable, subgroup or outcome/measurement	Definition and categories*
T2DM	Any of the below conditions: 
 • ICD-10 code E11 • ATC codes A10P or A10X • ATC codes A10A initiated at age>30 • ICD-10 codes E14 first recorded at age>30 without ATC code A10A in the previous 6 months

Abbreviations: ALT= alanine amino transferase; AST= aspartate amino transferase; Beta hCG=Beta subunit of human chorionic gonadotrophin; BMI= body mass index; eGFR= estimated glomular filtration rate; HDL-C= high density lipoprotein cholesterol; ICD-10= International classification of disease, 10th version; LDL-C= low density lipoprotein cholesterol; T2DM= type 2 diabetes mellitus; UK= United Kingdom.

* continuous variables will be also presented by means, SD, et cetera.

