9.3. Variables

Regardless of the coding system used in the database, different populations and subgroups of interest are defined as follows:

Treatment initiation with dulaglutide:

- any record of prescription of dulaglutide during the observation period without prior record of prescription of the same product in the available patient's history
- if no prior history is available to check the above criteria, the prescription is not considered as an initiation

Patients presenting with T2DM:

- with any recorded diagnosis code for T2DM
- or with any recorded treatment code for an ADM other than insulin
- or, with any recorded treatment code for insulin initiated at age >30 (defined as no record of insulin therapy during 6 months prior to first record of insulin treatment)
- or with any record of unspecified diabetes mellitus diagnosis at age >30 and without history of insulin therapy (defined as no record of insulin therapy during 6 months prior to first record of diabetes diagnosis),
- a sensitivity analysis will be conducted to determine the age threshold mentioned above (see section 9.7.3 Sensitivity analysis).

Patients with severe renal failure:

- with a recorded diagnosis of severe renal failure
- or with a recorded glomerular filtration rate (eGFR) value <30 ml/min/1.73 m²

Patients with hepatic disease:

- with a recorded diagnosis of any hepatic disorder

Patients with heart failure:

- with a recorded diagnosis of heart failure

Patients with severe gastrointestinal disease:

- with a recorded diagnosis of any of the following conditions:
 - cancer of the gastrointestinal tract,
 - diseases of the oesophagus,
 - active ulcer at the time of drug initiation (gastric, duodenal, gastro-jejunal, peptic ulcer of unspecified site),
 - active haemorrhagic gastritis, chronic atrophic gastritis, adult hypertrophic pyloric stenosis, obstruction of duodenum, and other motility disorders,
 - digestive fistula,
 - Crohn's disease, ulcerative colitis,
 - diverticular disease of the intestine,
 - severe vomiting, severe diarrhoea and severe constipation
 - motility disorders, including ileus, gastroparesis, et cetera,
 - infectious and inflammatory situations (appendicitis, cholecystitis, cholangitis).

Children and adolescents:

- Age < 18 at the time of treatment initiation
(subgroups of analysis: 0-4, 5-9, 10-14, and 15-17 years old).

Elderly:

- Age \geq 75 at the time of treatment initiation.

Pregnant and breastfeeding women:

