9.4.3. NPR and SPDR in Sweden

Swedish data combine data from the NPR, covering all specialist and hospital care in Sweden, and the SPDR, covering all drugs dispensed at pharmacies in Sweden. The national registers are

updated at least quarterly. These longitudinal data enable to find out comorbidities and historical clinical information on the subjects treated for their T2DM in a hospital, as well as drug prescription details (both primary and secondary care). Prescriptions are not formally linked to an ICD-10 code, but clinical input could provide rationale for linking prescriptions and diagnosis made in secondary care. However, information on patient anthropometric data (height, weight, BMI) are not available through the databases, nor are lab results and clinical measurements such as HbA1c, blood pressure and blood lipid levels.

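### The ICD-10 list in Table 9.3.2-1 does not implement the Section 9.3 definitions of severe renal failure and severe gastrointestinal disease, two subgroups of the primary objective

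*Protocol*

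**What the plan says.** Section 9.3 states the subgroup definitions and says that they apply whatever coding system a database uses. A patient has severe renal failure "with a recorded diagnosis of severe renal failure" "or with a recorded glomerular filtration rate (eGFR) value <30 ml/min/1.73 m²". Severe gastrointestinal disease is a list of ten items. One includes "adult hypertrophic pyloric stenosis, obstruction of duodenum, and other motility disorders" and another is "motility disorders, including ileus, gastroparesis, et cetera".

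Table 9.3.2-1 in Section 9.3.2 gives the ICD-10 codes that identify these subgroups. The renal entry is "ICD-10 code N18.5, N18.5". The gastrointestinal entry is C15-C26 followed by "K22.0, K22.1, K22.2 -K22.6, K23-K28, K29.0, K29.4 K50, K51, K55, K57". An eGFR below 30 appears in the table's laboratory block, to be used if available. Section 9.3.2 leaves only the CPRD Read codes to the SAP, so the ICD-10 codes are fixed in the protocol.

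For Sweden, Section 9.4.3 says that anthropometric data are not available, "nor are lab results and clinical measurements such as HbA1c, blood pressure and blood lipid levels". Table 9.4.5-1 likewise marks biological tests as unavailable there.

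**The concern.** Both subgroups are named in the primary objective, and Section 7 says they were chosen because few data exist on them. If the table is programmed as printed, patients who meet the text definition will be counted outside the subgroup, and some who do not meet it may be counted inside. Frequencies and patient profiles would then describe a group other than the one the protocol defines. Gastroparesis and ileus are of particular interest, because Section 7 describes the drug class as delaying gastric emptying. A Read code list built to correspond to this table could carry the same gaps into CPRD.

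**Working it through.** The plan gives no figure to reproduce on this point. The check compares text and table, using the standard meaning of each ICD-10 code.

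**Renal**

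- The two printed entries are one distinct code, N18.5 (stage 5, eGFR below 15).
- The text threshold of eGFR below 30 covers stage 4 (N18.4, 15 to 29) as well as stage 5.
- Section 9.3 names no stage. Stage 4 enters through the eGFR criterion, which is joined to the diagnosis by *or*.
- With the table as printed, a stage 4 patient is found only through a recorded eGFR.

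The effect can be written as: captured share = s + (1 − s) × q. Here s is the share of patients with eGFR below 30 who carry N18.5, and q is the probability that a qualifying eGFR is on record for the others. The documents give neither value. The inputs below are assumptions that show only how the result depends on q.

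| s | q = 0 (no laboratory data) | q = 0.80 | q = 0.95 |
|---|---|---|---|
| 0.10 | 0.10 | 0.10 + 0.90 × 0.80 = 0.82 | 0.955 |
| 0.25 | 0.25 | 0.25 + 0.75 × 0.80 = 0.85 | 0.963 |
| 0.40 | 0.40 | 0.40 + 0.60 × 0.80 = 0.88 | 0.970 |

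Without laboratory data the captured share falls to s. With good eGFR recording the missing code matters little.

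**Gastrointestinal**

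| Item in Section 9.3 | Covered by the table? |
|---|---|
| Gastrointestinal cancer | Yes (C15-C26, which also brings in C22, liver) |
| Oesophageal disease | In part: K22.0-K22.6 and K23, but not K20, K21, K22.7 or K22.8 |
| Active ulcer | Yes (K25-K28) |
| Gastritis, stenosis, obstruction | In part: K29.0 and K29.4, but not pyloric stenosis (K31.1) or duodenal obstruction (K31.5) |
| Digestive fistula | No (e.g. K31.6, K63.2) |
| Crohn's disease, ulcerative colitis | Yes (K50, K51) |
| Diverticular disease | Yes (K57) |
| Severe vomiting, diarrhoea, constipation | No (R11; K59.1 or R19.7; K59.0) |
| Motility disorders | Oesophageal ones in part (K22); not ileus (K56.0, K56.7) or gastroparesis (K31.8) |
| Appendicitis, cholecystitis, cholangitis | No (K35-K37; K81; K83.0) |

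Four of the ten items are covered and six are wholly or partly uncovered. In the other direction, K55 matches no item in the text, and C22 is also in the table's hepatic list. No laboratory criterion makes up for the missing gastrointestinal codes in any ICD-10 database.

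**The case against.** The strongest reply is that the text definition is intact and governs, so the table is only an implementation that needs aligning. The feasibility step in Section 9.5.2 also checks the availability and validity of each variable. That is fair, but Section 9.3.2 defers only the Read codes, and nothing in the protocol says that the ICD-10 list will be revised.

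On the renal row, the duplicate might be a one-digit error in reading the PDF. If the source table prints N18.4, the renal half falls and the gastrointestinal half remains. A reader might also infer a renal under-count in every country. The documents do not support that, because the eGFR criterion recovers stage 4 patients wherever a value is recorded. Nor is recovery complete outside Sweden, since Section 9.9.1 says laboratory values are not available for all patients. Sweden itself is only a candidate, although a likely one: Table 9.3.2-1 names it among the first three countries, the mock table is headed with it, and Table 9.5.2-1 gives it the largest GLP-1 RA count (about 12,000).

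A reader might further infer that a difference between countries would be an artefact of coding. The plan makes no such formal comparison: Section 9.7.1 rules out pooling, citing differences in coding among its reasons, and plans no inference. Section 9.9.1 does admit renal false negatives, but attributes them to unrecorded eGFR and not to the code list.

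On the gastrointestinal row, leaving out symptom codes may be deliberate. R11 and K59 carry no severity grade, and Section 9.9.1 says severity can hardly be identified. This objection stands against adding those codes without restriction.

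**Conclusion.** The mismatch between definition and code list holds for both subgroups and should be corrected before extraction. For renal failure the direction is clear: stage 4 is lost to the diagnosis route. The loss is full where no laboratory values exist, and elsewhere confined to patients without a recorded qualifying eGFR. For gastrointestinal disease, the named conditions listed above are missed in every ICD-10 database.

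It is tempting to conclude that the gastrointestinal subgroup as a whole is under-counted. That is not shown, because K55 and C22 add patients while other codes are absent. No number of misclassified patients can be given for either subgroup: the documents report no stage distribution, eGFR recording rate or condition frequencies, and counting list items does not measure patients. The conclusion rests on the standard meaning of the ICD-10 codes and on the table being printed as it reads here. The study-size calculation is unaffected.

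**What to change.** Reconcile Section 9.3 with Table 9.3.2-1 before extraction:

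- **Renal:** replace the duplicated entry with N18.4, N18.5.
- **Gastrointestinal conditions that ICD-10 can identify:** add codes, for example K31.1, K31.5, K31.6, K31.8 (noting that it is not specific to gastroparesis), K35-K37, K56, K63.2, and codes for cholecystitis (K81) and cholangitis (K83.0). Replace the open-ended motility item with a closed list.
- **Oesophagus:** either widen the codes to match the text or narrow the text to the conditions coded.
- **Severe vomiting, diarrhoea and constipation:** either state that severity cannot be identified and remove them from the definition, or report them separately. Do not add R11 and K59 without restriction.
- **K55 and C22:** drop them from the gastrointestinal row or justify them.
- **CPRD:** derive the Read codes from the corrected list.

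The cost is an edit to text and code list. No new data are needed.
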